7.11 Laboratory Assessments

Local laboratories will perform the following laboratory tests, and results will be provided to the Investigator. Blood and urine samples for hematology, chemistry, activated partial thromboplastin (aPTT) and International Normalized Ratio (INR) or Prothrombin (PT), thyroid function, and urinalysis will be prepared using standard procedures. Laboratory panels are defined as follows:

Hematology	WBC count with differential, RBC count, hemoglobin, hematocrit, reticulocyte count, and platelet count
Chemistry	albumin, ALP, ALT, AST, BUN, calcium, carbon dioxide, chloride, creatinine, glucose, potassium, sodium, total bilirubin, lactate dehydrogenase, and total protein
Coagulation Tests:	aPTT and International Normalized Ratio (INR) or PT
Thyroid Function Test	TSH, free T3, and free T4
Urinalysis	appearance, color, pH, specific gravity, ketones, protein, glucose, bilirubin, nitrite, urobilinogen, and occult blood (microscopic examination of sediment will be performed only if the results of the urinalysis dipstick evaluation are positive)
Pregnancy Test	Serum or urine pregnancy test for women of child bearing potential

Abnormalities in clinical laboratory tests that lead to a change in patient management (ie, dose withhold or modification, requirement for additional medication or monitoring) are considered clinically significant for the purposes of this trial and will be recorded on the AE CRF page. If values meet criteria defining them as serious, they must be reported as SAEs (Section 9.1.2).

7.12 Pharmacokinetics

Blood samples for PK with sparse sampling techniques will be obtained on all patients on Arm 1 (including crossover patients). Serum samples will be collected to characterize PK of AM0010 in combination with pembrolizumab and to explore exposure-safety and exposure-efficacy relationships. Data from these investigations may be evaluated for correlations with response, survival, and safety data.

PK samples will be drawn pre-dose (AM0010 and pembrolizumab)

- Day 1 of Cycles 1, 2, 3, 4, and every fourth cycle thereafter (eg, 8, 12, 16, etc.)
- End of treatment visit
- Day-60 and -90 follow-up visits after the last dose of study treatment.

Bioanalytical samples collected to measure investigational product concentration will be retained for a maximum of 1 year following last participant visit for the study.

7.13 Immunogenicity (ADA [anti-drug antibodies])

Blood samples for immunogenicity analysis will be obtained on all patients on Arms 1 and 2 (including crossover patients). Samples will be evaluated for development of anti-drug antibodies (ADAs) by a validated immunoassay.

ADA samples will be drawn pre-dose at the following time points:

- Day 1 of Cycles 1, 2, 3, 4, and every fourth cycle thereafter (eg, 8, 12, 16, etc.)
- End of treatment visit

- Day-60 and -90 follow-up visits after the last dose of study treatment.

All immunogenicity samples will be retained for a maximum of 15 years after the last participant visit, or for a shorter period if local regulations and Ethical Review Boards (ERBs) allow, at a facility selected by the sponsor. The duration allows the sponsor to respond to future regulatory requests related to the investigational product. Any samples remaining after 15 years will be destroyed.

7.14 Biomarkers

Blood samples for biomarker analysis will be obtained on all patients in Arms 1 and 2. A variety of factors that may impact the immunomodulatory properties and efficacy of AM0010 in combination with pembrolizumab will be investigated in peripheral blood. Data from these investigations may be evaluated for correlations with response, survival, and safety data.

- Biomarker samples will be drawn pre-dose (AM0010 and pembrolizumab) on Day 1 of Cycles 1, 2, 3, 5, 7, 9, 11, etc. and at the end of treatment visit.

All biomarker samples (both tissue and blood) will be retained for a maximum of 15 years after the last participant visit, or for a shorter period if local regulations and ERBs allow, at a facility selected by the sponsor. The duration allows the sponsor to respond to future regulatory requests related to the investigational product. Any samples remaining after 15 years will be destroyed.

8.0 REMOVAL AND REPLACEMENT OF PATIENTS

8.1 Removal of Patients

Patients have the right to withdraw from the trial at any time and for any reason without prejudice to his or her future medical care by the physician or at the institution.

Any patient who withdraws consent to participate in the trial will be removed from the trial immediately upon the date of request. The Investigator will make every effort to contact the patient and perform end-of-treatment procedures. Should a patient (or a legally acceptable representative) request or decide to withdraw from the trial, all efforts will be made to complete and report the observations as thoroughly as possible in addition to follow up for OS. All information should be reported on the applicable CRFs.

The patient who requests to stop trial treatment or has withdrawn from trial treatment because of the Investigator's or Sponsor's concern before completion of the protocol-specified treatment duration will be strongly encouraged to continue the schedule of trial observations, in addition to follow up for OS.

If the patient has withdrawn because of toxicities, the Investigator should arrange for the patient to be followed for a minimum of 90 days or until any drug-related toxicities resolve to grade 1 according to CTCAE Version 4.03, or return to the patients' baseline values, in addition to follow up for OS. All end-of-treatment procedures should be completed for such a patient.

Reasons for removal from investigational product or observation may include:

- Withdrawal of consent
- Administrative decision by the Investigator or Sponsor
- The patient's physician feels it is no longer in their best interest of the patient to continue on treatment.
- Require subsequent systemic anticancer therapy
- Pregnancy (report on Pregnancy Notification Worksheet/CRF)
- Ineligibility determined after enrollment
- Significant protocol deviation
- Patient noncompliance
- Adverse event (disease progression is not considered an AE)
- Progression of disease (clinical and/or radiological)
- Lost to follow-up

The reason for withdrawal, the date of administration of the final trial treatment, and the date of withdrawal should be recorded on the End-of-Treatment CRF.

All randomized patients will be followed for OS every 9 weeks (± 7 days) during the first year from the 90-day follow-up visit, every 12 weeks (± 7 days) during the second year, and every 16 weeks (± 7 days) thereafter. The survival follow-up will be conducted until death or study completion, whichever is first, whether or not trial treatment was administered.

For patients who were randomized, but withdraw consent, survival (date of death) will be obtained by use of publicly available information.

All randomized patients who discontinue trial treatment before disease progression or patients randomized but not treated will be followed for PFS per protocol until study completion, disease progression, or death or receipt of new anti-cancer therapy, whichever is first. Scans will include head and CAPs and will be sent to the central imaging vendor for archiving and possible assessment at a later date. If clinical progression is suspected, all relevant clinical documentation is to be submitted to the central imaging vendor for archiving.

The Investigator (or designee) will acquire the following information from patients who were randomized:

- Tumor assessment for all randomized patients who discontinue the trial treatment before disease progression or patients randomized but not treated. Tumor assessment will be repeated until study completion, disease progression, death or receipt of new anti-cancer therapy, whichever is first.
- Subsequent cancer treatments (all randomized patients).
- Any SAEs considered to be related to trial treatment, follow until resolution.
- Date and cause of death (all randomized patients).

8.2 Replacement of Patients

Randomized patients who withdraw from the trial will not be replaced.

9.0 ADVERSE EVENT REPORTING

9.1 Definitions

9.1.1 Adverse Events

An adverse event (AE) is defined as any untoward medical occurrence in a patient or clinical investigation subject administered a pharmaceutical product that does not necessarily have a causal relationship with this treatment. An adverse event can therefore be any unfavorable and unintended sign (including an abnormal laboratory finding), symptom, or disease temporally associated with the use of a medicinal (investigational) product, whether or not related to the medicinal (investigational) product.

Investigators are responsible for:

- monitoring the safety of patients in this study and for alerting Lilly or its designee to any event that seems unusual, even if this event may be considered an unanticipated benefit to the patient,
- the appropriate medical care of patients during the study,
- documenting their review of each laboratory safety report, and
- following, through an appropriate healthcare option, AEs that are serious or otherwise medically important, considered related to study treatment or the study, or that caused the patient to discontinue study treatment before completing the study. The patient should be followed until the event resolves, stabilizes with appropriate diagnostic evaluation, or is reasonably explained. Frequency of follow-up evaluation is left to the discretion of the investigator.

A worsening of an existing medical condition occurs when a condition present at the time the informed consent form is signed (eg, diabetes, migraine headaches, gout) becomes more severe, more frequent, or increases in duration during investigational product treatment.

Abnormal laboratory values should not be reported as an AE, unless they are considered clinically significant by the Investigator; however, any clinical consequences of the abnormality should be reported as an AE. Abnormalities in clinical laboratory tests that lead to a change in patient management (ie, dose schedule reduction or withhold, requirement for additional medication or monitoring) are considered clinically significant for the purposes of this trial and will be recorded on the AE CRF page.

Lack of drug effect is not an AE in clinical studies, because the purpose of the clinical study is to establish treatment effect.

Planned surgeries and nonsurgical interventions should not be reported as AEs unless the underlying medical condition has worsened during the course of the study.

If a study patient experiences elevated $ALT \geq 5 \times ULN$ and elevated total bilirubin $\geq 2 \times ULN$, or $ALT \geq 8 \times ULN$, liver tests ([Appendix E](#)), including ALT, AST, total bilirubin, direct bilirubin, gamma-glutamyl transferase (GGT), and creatine phosphokinase (CPK), should be repeated within 3 to 5 days to confirm the abnormality and to determine if it is increasing or

decreasing. If the abnormality persists or worsens, clinical and laboratory monitoring should be initiated by the investigator, based on the hepatic monitoring tests ([Appendix E](#)) and in consultation with the Lilly Clinical Research Physician (CRP). Monitoring of ALT, AST, and total bilirubin should continue until levels normalize or return to approximate baseline levels.

9.1.2 Serious Adverse Events

An SAE is any AE from this study that results in 1 of the following outcomes:

- death
- initial or prolonged inpatient hospitalization
- a life-threatening experience (ie, immediate risk of dying)
- persistent or significant disability/incapacity
- congenital anomaly/birth defect
- important medical events that may not be immediately life-threatening or result in death or require hospitalization may be considered serious when, based upon appropriate medical judgment, they may jeopardize the patient and may require intervention to prevent 1 of the other outcomes listed in the definition above.

9.2 Suspected Unexpected Serious Adverse Reactions

Suspected unexpected serious adverse reactions (SUSARs) are serious events that are not listed in the IB and that the investigator identifies as related to study treatment or study procedure. United States 21 CFR 312.32 and Regulation (EU) No. 536/2014 and the associated detailed guidances or national regulatory requirements in participating countries require the reporting of SUSARs. Lilly has procedures that will be followed for the recording and expedited reporting of SUSARs that are consistent with global regulations and associated detailed guidances.

9.2.1 Pregnancy

Pregnancy (during maternal or paternal exposure to study treatment) does not meet the definition of an AE, but should be reported. However, to fulfill regulatory requirements any pregnancy should be reported following the SAE process to collect data on the outcome for both mother and fetus.

The Investigator will inform Lilly within 24 hours of awareness by any study personnel of any case of pregnancy and collect information on any exposure to the study drug(s) during pregnancy (female patient or male patient's partner). An exposure during pregnancy (also referred to as exposure in utero) occurs if a female is or has been found to be pregnant after being exposed to the study drug(s) directly, indirectly, or via her partner (paternal exposure). If any study subject becomes or is found to be pregnant and exposed to investigational product as described above, the Investigator must submit this information to Lilly on a

Pregnancy Report Form irrespective of whether an AE has occurred and within 24 hours of awareness of the pregnancy. The information submitted should include the anticipated date of delivery. Follow-up is conducted to obtain pregnancy outcome information on all exposure during pregnancy reports with an unknown outcome. The Investigator will follow the pregnancy until completion or until pregnancy termination (ie, induced abortion) and then notify Lilly of the outcome. The Investigator will provide this information as a follow-up to the initial Pregnancy Report Form. The reason(s) for an induced abortion should be specified. A report is not created when an ectopic pregnancy report is received since this type of pregnancy is not usually viable. Rather, an SAE case is created with the event of ectopic pregnancy. If the outcome of the pregnancy meets the criteria for immediate classification as an SAE (ie, spontaneous abortion, stillbirth, neonatal death, or congenital anomaly [including that in an aborted fetus, still birth, or neonatal death]), the Investigator should follow the procedures for reporting SAEs. In the case of a live birth, the “normality” of the newborn can be assessed at the time of birth (ie, no minimum follow-up period of a presumably normal infant is required before a Pregnancy Report Form can be completed), and birth information will be provided as a follow-up of the initial Pregnancy Report Form. Case processing at Lilly will be performed as described above for SAE reports. Additional information regarding the exposure during pregnancy may be requested from the Investigator. Further follow-up of birth outcomes will be handled on a case-by-case basis (eg, follow-up on preterm infants to identify developmental withhold).

9.3 Reporting Procedures for All Adverse Events

After the ICF is signed, study site personnel will record via electronic case report form (eCRF) the occurrence and nature of each patient’s preexisting conditions, including clinically significant signs and symptoms of the disease under treatment in the study. In addition, study site personnel will record via eCRF any change in the preexisting conditions and any new conditions as AEs. Investigators should record their assessment of the potential relatedness of each AE to study treatment via eCRF.

All AEs, regardless of grade and occurring after obtaining informed consent, observed by the Investigator or reported by the patient (whether or not attributed to investigational product), will be reported on the AE CRF. Please note that disease progression should not be considered an AE, but shall be documented on the appropriate CRF.

Medically significant AEs considered to be related to the investigational product by the Investigator or Sponsor will be followed until resolved or considered stable. The Investigator must assign the following attributes: description (concise diagnosis, if available); dates of onset and resolution; severity; assessment of relatedness to investigational product; and action taken. The Investigator may be asked to provide follow-up information, medical records, and extracts from medical records or CRFs.

The SAE reporting to Lilly or its designee begins after the patient has signed the ICF and has received study treatment. However, if an SAE occurs after signing the ICF, but prior to

receiving study treatment, it needs to be reported ONLY if it is considered reasonably possibly related to study procedure. “Death” as an outcome of an AE may occur and should not be reported as an AE, but the cause of death should be reported on the AE eCRF.

For the purpose of this study, progression of underlying malignancy is not considered an (S)AE. Hospitalization, prolonged hospitalization, or death due solely to the progression of underlying malignancy will be captured on the AE CRF, but will NOT be reported as an SAE. Clinical symptoms of progression may be reported as AEs if they cannot be determined to be exclusively due to the progression, or if they do not fit the expected pattern of progression for late stage NSCLC cancer.

SAEs which are considered related to study drug occurring >90 days after last trial treatment must be reported on both a CRF and on a SAE Report Form (with an autopsy report if available).

Investigators are not obligated to actively seek AEs or SAEs in patients once they have discontinued (the patient summary CRF has been completed). However, if the investigator learns of any SAE, including a death, at any time after a patient has been discontinued from the study, and he/she considers the event reasonably possibly related to the study treatment or study participation, the investigator must promptly notify Lilly or its designee.

Lilly will periodically review evolving aggregate safety data within the study by appropriate methods.

If it is deemed to be in the best interest of the patient to start a new anti-cancer treatment prior to the follow-up visit, the visit duration may be shortened. In this case, the follow-up assessments should be completed prior to the initiation of the new therapy. If an anti-tumor treatment is initiated within 90 days of the last dose of trial treatment, the start date of this treatment should be documented on the appropriate CRF.

The Investigator must notify the IRB of SAEs occurring at the site and other AE reports received from Lilly/designee in accordance with local procedures/site IRB policies.

It will be left to the Investigator’s clinical judgment whether or not an AE is of sufficient severity to require the patient’s removal from treatment. A patient may also voluntarily withdraw from treatment due to what he or she perceives as an intolerable AE. If either of these occurs, the patient must undergo an end-of-treatment assessment and be given appropriate care under medical supervision until symptoms cease or the condition becomes stable. If the patient is permanently withdrawn from the trial or investigational product due to an SAE, this information must be included in either the initial or follow-up SAE Report Form or the End-of-Treatment CRF.

Study site personnel must report any treatment discontinuations that result from AEs to Lilly or its designee via eCRF, clarifying, if possible, the circumstances leading to the discontinuation of treatment.

The trial will use the Common Terminology Criteria for grading AEs that are experienced by research patients. If the AE is not specified in the NCI-CTCAE v4.03 (https://ctep.cancer.gov/protocolDevelopment/electronic_applications/ctc.htm#ctc_50) the severity will be assessed on the following scale with appropriate clinical definitions:

1 = mild, 2 = moderate, 3 = severe, 4 = life threatening, 5 = fatal

The investigator will interpret and document whether or not an AE has a reasonable possibility of being related to study treatment or a study procedure, taking into account the disease, concomitant treatments, or pathologies.

The relationship of the AE to the investigational product will be assessed by means of the question: 'Is there a reasonable possibility that the event may have been caused by the investigational product?' Answer Yes or No.

Determination of expectedness will be based on the contents of the Investigator's Brochure.

The Medical Dictionary for Regulatory Activities (MedDRA) will be used to classify the events.

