**6.6.2. Adverse Events**

Adverse event terms will be mapped using MedDRA. Adverse events will be graded according to the National Cancer Institute (NCI) – A Common Terminology Criteria for Adverse Events (CTCAE) v 4.03.

Pre-existing conditions are defined as AEs that begin prior to the first dose of study drug.

A treatment emergent adverse event (TEAE) is defined as any AE that begins between the day of first dose and 30 days after treatment discontinuation (or up to any time if serious and related to study treatment), or any pre-existing condition that increases in CTCAE grade between the day of first dose and 30 days after treatment discontinuation (or up to any time if serious and related to study treatment).

Related AEs in patients treated with AM0010 in combination with pembrolizumab are defined as either related to AM0010 or related to pembrolizumab or both AM0010 and pembrolizumab.

The following TEAE/serious adverse events (SAE) outputs will be produced:

- a. overview of TEAEs
- b. summary of TEAEs by Preferred Terms (PTs) (all grade and grade  $\geq 3$ )
- c. summary of TEAEs by System Organ Class (SOC) and PT (all grade and grade  $\geq 3$ )

- d. summary of TEAEs by PT and Maximum Grade
- e. listing of SAEs
- f. summary of SAEs by SOC and PT (all grade and grade  $\geq 3$ )
- g. listing of TEAEs leading to study treatment discontinuation

Summaries b, c, d, and f will be produced for the related TEAEs/SAEs.

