#### 6.7.4. Crossover Patients

Patients in Arm 2 (pembrolizumab) who crossover to Arm 1 (AM0010 in combination with pembrolizumab) following documented disease progression will be analyzed accordingly if data warrants.

For patients who crossover to Arm 1 after documented disease progression on pembrolizumab, time to progression while on pembrolizumab will be compared to the time to progression following crossover, where the time to progression following crossover is defined as the time from time of crossover to the earliest documented disease progression. The last available tumor assessment before crossover will serve as the baseline for disease assessment post crossover. If the number of events permits, time to progression before and after crossover will be summarized descriptively using the Kaplan-Meier method.

Patients who crossover to the AM0010 in combination with pembrolizumab are censored at time of crossover (ie, AEs occurring during treatment with AM0010+pembrolizumab are excluded or control arm (pembrolizumab) patents). An exploratory safety analysis may be conducted for the crossover patients including all adverse events starting from the date of first dose of AM0010+pembrolizumab.

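### Protocol 9.3 says progression is not an adverse event yet sends progression-only hospitalizations and deaths to the AE form, and no rule keeps those records out of the TEAE tables

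*Protocol*

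**What the plan says.** Protocol 9.3 gives three instructions on progression.

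- Progression itself: "Please note that disease progression should not be considered an AE, but shall be documented on the appropriate CRF". Later in the section, "progression of underlying malignancy is not considered an (S)AE". Protocol 8.1 also says that progression is not an AE.
- Its consequences: "Hospitalization, prolonged hospitalization, or death due solely to the progression of underlying malignancy will be captured on the AE CRF". The same sentence keeps such events out of SAE reporting.
- Its symptoms: "Clinical symptoms of progression may be reported as AEs if they cannot be determined to be exclusively due to the progression". Symptoms that are atypical for late-stage disease may also be reported.

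The section adds that death as an outcome is not itself to be reported as an AE, but that its cause goes on the AE eCRF.

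For the analysis, SAP 6.6.2 says that a TEAE "is defined as any AE that begins between the day of first dose and 30 days after treatment discontinuation", with a longer allowance for serious related events. It summarizes TEAEs by preferred term, by system organ class and by maximum grade, including grade 3 or higher. Protocol 10.6.6 tabulates TEAEs of any cause and runs the window to 90 days after the last dose; the protocol synopsis uses 30 days.

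For Arm 2 patients who cross over, SAP 6.7.4 censors at crossover, so that "AEs occurring during treatment with AM0010+pembrolizumab are excluded" from the control arm. Protocol 7.8.1 allows no more than 21 days between progression on the scan and crossover. Arm 1 patients stop treatment at progression and continue in follow-up (protocol 3.0).

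**The concern.** A site that follows 9.3 puts a progression-only hospitalization or death on the AE form, and a programmer who follows SAP 6.6.2 counts what is on that form. The result is a TEAE with a serious outcome that is not an SAE, although protocol 9.1.2 makes any AE leading to death or inpatient hospitalization serious. The TEAE and SAE outputs would then not reconcile.

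Safety and tolerability is a secondary objective, and safety is a main purpose of the interim analysis. With about 50 patients per arm, each patient is 2 percentage points. If disease outcomes sit in the TEAE and grade 3 or higher tables, the comparison of arms reflects efficacy as well as toxicity. The arms are also followed differently after progression, so the mixture need not be the same in each.

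**Working it through.** **Text check**

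| Item | Protocol 9.3 | SAP 6.6.2 / protocol 10.6.6 |
|---|---|---|
| Progression | Not an AE or SAE; other form | Not mentioned |
| Symptom due only to progression, of expected pattern | Not an AE | Not mentioned |
| Hospitalization due only to progression | AE form, not SAE | No exclusion or flag |
| Death due only to progression | AE form, not SAE; cause on AE eCRF | No exclusion or flag |

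So a symptom is kept off the form while the hospitalization that it causes goes on it. For a progression death, the cause to be entered on the AE form is the very progression that the section says is not an AE. Grade 5 means fatal (protocol 9.3). A fatal record would therefore fall inside the SAP's grade 3 or higher and maximum-grade tables, but outside the Grade 1 to 4 and Grades 3 and 4 intensity summaries named in protocol 10.6.6.

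**Size of a possible imbalance**

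The plan gives no figure, so this is an illustration.

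Inputs from the documents: about 50 patients per arm; control median PFS 10.3 months (the phase 3 trial cited in protocol 1.1); at most 21 days from progression to crossover; a 30-day or 90-day window.

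Assumptions: exponential PFS; progression counted to 12 months; last dose at progression; hazard h of a progression-only hospitalization or death after progression, taken as 0.10 per month (range 0.05 to 0.20); a share c of Arm 2 progressors crossing over, at day 21; at most one record per patient.

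1. Progressed by 12 months with no treatment effect: 1 − exp(−ln 2 × 12/10.3) = 0.554, or 50 × 0.554 = 27.7 patients per arm.
2. Probability of a record within d days, 1 − exp(−0.10 × d/30.4375): 0.0667 at 21 days, 0.0939 at 30 and 0.2560 at 90.
3. Arm 1 records = 27.7 × P(window).
4. Arm 2 records = 27.7 × [c × P(21) + (1 − c) × P(window)].

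At c = 0.6:

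- 30 days: Arm 1 is 27.7 × 0.0939 = 2.60. Arm 2 is 27.7 × (0.6 × 0.0667 + 0.4 × 0.0939) = 2.15. The difference is 0.45 records, or 0.9 points.
- 90 days: Arm 1 is 27.7 × 0.2560 = 7.09. Arm 2 is 27.7 × (0.6 × 0.0667 + 0.4 × 0.2560) = 3.94. The difference is 3.15 records, or 6.3 points.

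Expected records, Arm 1 vs Arm 2, with the difference in points (2 × records):

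| PFS hazard ratio | Crossover | 30-day window | 90-day window |
|---|---|---|---|
| 1 | 0% | equal | equal |
| 1 | 30% | 2.60 vs 2.37 (+0.5) | 7.09 vs 5.52 (+3.1) |
| 1 | 60% | 2.60 vs 2.15 (+0.9) | 7.09 vs 3.94 (+6.3) |
| 1 | 90% | 2.60 vs 1.92 (+1.4) | 7.09 vs 2.37 (+9.4) |
| 0.7 | 60% | 2.03 vs 2.15 (−0.2) | 5.53 vs 3.94 (+3.2) |
| 0.5 | 60% | 1.56 vs 2.15 (−1.2) | 4.25 vs 3.94 (+0.6) |
| 0.5 | 30% | 1.56 vs 2.37 (−1.6) | 4.25 vs 5.52 (−2.5) |

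Further sensitivity at hazard ratio 1 and 60% crossover:

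- h from 0.05 to 0.20: the difference runs from 0.5 points (1.33 vs 1.10) to 1.7 (4.96 vs 4.12) with 30 days, and from 3.4 points (3.81 vs 2.09) to 10.6 (12.37 vs 7.09) with 90 days.
- If those who cross over are fitter (0.03 per month against 0.10 overall), the ratio of Arm 1 to Arm 2 falls from 1.21 to 1.06 with 30 days, and from 1.80 to 1.20 with 90 days.
- If crossover comes at day 7, the 30-day ratio rises to 0.0939/0.0512 = 1.83.

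At 60% crossover and h = 0.10, Arm 1 has more records only if its share of progressors relative to Arm 2 exceeds 0.83 (30 days) or 0.56 (90 days).

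**The case against.** The strongest reply is that capture on a form is not classification. Protocol 9.3 says that progression is not an AE, and the SAP definition starts from AEs, so a careful programmer could drop these records. That stands to this extent: the documents do not say that the records are counted, only that nothing stops them. No field or rule for removing them is stated, and two programmers could produce different tables. The CRF is not among the documents, so a flag may already exist.

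Second, part of the problem is already contained. The main TEAE and SAE summaries are repeated for related events, where progression-only records should fall out. Deaths are listed with cause (SAP 6.6.3), hospitalizations have their own summary (SAP 6.6.11), and the safety analysis is descriptive. The SAP lists no separate table of fatal TEAEs. All this is correct, but the any-cause tables remain open.

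Third, a reader might infer a built-in excess of such events in the AM0010 arm. The documents do not support that. They support a longer counting period per progressed patient in Arm 1 than for Arm 2 patients who cross over. The net count also depends on how many cross over (it is optional), who they are, which window applies, and whether Arm 1 has fewer progressions, as an effective drug would produce. Nor does the cited 80.2% six-month survival give a scale: 50 × (1 − 0.802) = 9.9 deaths per arm, but these are deaths from any cause, not progression-only deaths inside a TEAE window.

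Fourth, the unequal follow-up comes from SAP 6.7.4, not from 9.3. It applies to every type of AE and keeps AM0010 toxicity from being charged to pembrolizumab alone. That also stands.

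**Conclusion.** The contradiction in protocol 9.3 is real, and no later rule resolves it. Progression-only hospitalizations and deaths can enter the all-grade, maximum-grade and grade 3 or higher TEAE tables without a matching SAE.

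The effect on the comparison of arms is uncertain in size and sign. Under equal progression, 0.10 events per month and 60% crossover, it is about 1 point against Arm 1 with the 30-day window and about 6 points with the 90-day window. At a PFS hazard ratio of 0.7 it is slightly reversed with 30 days and about 3 points against Arm 1 with 90 days. The event rate, crossover share and hazard ratios are assumptions. Either direction is unwelcome: without a delay in progression Arm 1 can look more toxic than it is, and with one, fewer progression records can hide added toxicity.

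This is more than a missing detail, because a stated recording rule conflicts with the protocol's own position on what an AE is. It is not evidence of a fixed bias against AM0010.

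**What to change.** 1. Reconcile protocol 9.3: record hospitalizations and deaths due solely to progression off the AE form, or keep them there with a flag for that cause. Align the sentence on cause of death.
2. State in SAP 6.6.2 that such records are excluded, in both arms, from the TEAE and grade 3 or higher summaries (maximum-grade table included) and listed separately with the deaths of SAP 6.6.3. Add one supplementary table that includes them.
3. Use one TEAE window in the protocol synopsis, protocol 10.6.6 and SAP 6.6.2.

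The cost is one CRF flag or programming rule and a few sentences. The interim data cut-off (18 March 2019) has passed, but the rule can govern later analyses. The downside is small: whether an event is due solely to progression is an investigator's judgment in an open-label trial, and the tables with and without these records make its influence visible. The flag does not remove the general cut of Arm 2 AEs at crossover, which should be stated beside the tables.
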